12.1.1.3 Hypotheses and Sample Size Justification

Initial cohort:

No hypotheses will be tested, only observational, summary statistics will be performed.

Continued enrollment cohort:

A systematic literature search was conducted on PubMed and Embase from January 1, 2016 to September 2022 to identify studies that evaluated the safety and effectiveness of an endoscopic clip device for closing various types of incisions, lesions, or defects in the gastrointestinal tract resulting from endoscopic mucosal resection (EMR), endoscopic submucosal dissection (ESD), polypectomy of polyps or adenomas, perforations, and fistulas. The primary objective of the search strategy was to identify studies that examined the closure of large mucosal defects by endoscopic clipping. Twenty studies were identified through a post-market literature review activity were included to the analysis with a total of 2257 patients.

We hypothesize that the **clinical success rate** of MANTISTM clip will be greater than the performance goal of **89%** with expected clinical success rate of **94%**. These assumptions are based in the following meta-analyses of clinical success for closure of a defect:

• 20 publications representing 2257 patients: 93.9% (95% CI 88.6%-97.6%)

We hypothesize that the **serious adverse event (SAE) rate** related to MANTISTM clip or the endoscopic clipping portion of the procedure will be lower than the performance goal of **19%** with expected related SAE rate of **10%**. These assumptions are based in the following meta-analyses of clinical success for closure of a defect:

- 9 publications representing 1019 patients: 9.8% (95% CI 3.7%-18.5%)
 - 12.2 Using an exact test with an alpha level of 0.05, 217 subjects enrolled will provide at least 80% power for the performance and safety metrics. An additional 10% will be added for attrition, so total enrollment will be 240 subjects. These tests will only be performed for cases in the continued enrollment cohort General Statistical Methods

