11.8 Study Completion

Subjects will be followed for 30 days (\pm 5 days) post index procedure. Subjects will continue to receive care from their doctor as they normally would. At study completion, an End of Study form will be completed, indicating whether the subject completed the study. If the last follow-up visit was not completed, the reason will be noted on the study completion form (e.g. subject withdrawn by investigator, subject withdrew consent, lost to follow-up, AE, death, etc.) and a Protocol Deviation form will be completed.

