12.2.1 Analysis Sets

Enrolled Cohort

A subject is considered enrolled after signing the study-specific ICF. Subjects who sign the ICF, but subsequently do not meet one or more of the eligibility criteria provided in Section 8.1 and Section 8.2 will be considered screen failures and excluded from the study.

Intent-to-Treat Cohort (ITT)

This cohort consists of enrolled subjects who are planned to have a MANTISTM clip placed regardless if they met I/E criteria.

Treated Cohort

The treated cohort is a subset of the ITT subjects who have a MANTISTM clip placed.

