Statistical Analysis Plan

Prospective, Multi-Center, All-Comer MANTIS Endoscopic **Clipping Study**

MANTIS Clip Study

E7170

CONFIDENTIAL DO NOT COPY OR DISTRIBUTE WITHOUT WRITTEN PERMISSION

APPROVALS (Check/Complete one below):	
Approvals are captured electronically	
An electronic system for capturing approvals is not being signatures are captured below:	g used for this study; wet
Lead Biostatistician – [Insert Name and Title]	Date (dd-mon-yyyy)
Clinical Project/Trial Manager – [Insert Name and Title]	Date (dd-mon-yyyy)
Medical Director - [Insert Name and Title]	Date (dd-mon-yyyyy)

Revision History

Document Revision Number	Template Number and Version	Section	Change	Reason for Change
1	В	1, 3.1.3	Changed alpha level from 0.05 to 0.025	This was a typo in the protocol that was transferred to SAP. The sample size calculation was performed using 0.025 alpha, so nothing else changed.
2	С	1, 3, 5.5	Match protocol version C	Updating to match version C of the protocol

TABLE OF CONTENTS

1	PROTOCOL SUMMARY			
2	INT	TRODUCTION	8	
3	EN	DPOINT ANALYSIS	8	
	3.1	Primary Endpoints	8	
	P	rimary Effectiveness Endpoint	8	
	3.1.	1	8	
	3.1.	2 Primary Safety Endpoint	8	
		3 Hypotheses and Sample Size		
4	GE	NERAL STATISTICAL METHODS	, S	
	4.1	Analysis Sets		
5	AD	DITIONAL DATA ANALYSES		
	5.1	Other Endpoints/Measurements		
	5.2	Baseline Data		
	5.3	Procedure Data		
	5.4	Post-Procedure Data		
	5.5	Interim Analyses		
	5.6	Subgroup Analyses		
	5.7	Justification of Pooling		
	5.8	Multivariable Analyses		
_	5.9	Changes to Planned Analyses		
6		idation		
7		gramming Considerations		
	7.1	Statistical Software		
	7.2	Format of output		
	73	Rules and Definitions	1 1	

PROTOCOL SUMMARY

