3.1.3 Hypotheses and Sample Size

Initial cohort:

No hypotheses will be tested, only observational, summary statistics will be performed.

Continued enrollment cohort:

A systematic literature search was conducted on PubMed and Embase from January 1, 2016 to September 2022 to identify studies that evaluated the safety and effectiveness of an endoscopic clip device for closing various types of incisions, lesions, or defects in the gastrointestinal tract resulting from endoscopic mucosal resection (EMR), endoscopic submucosal dissection (ESD), polypectomy of polyps or adenomas, perforations, and fistulas. The primary objective of the search strategy was to identify studies that examined the closure of large mucosal defects by endoscopic clipping. Twenty studies

were identified through a post-market literature review activity were included to the analysis with a total of 2257 patients.

We hypothesize that the **clinical success rate** of MANTISTM clip will be greater than the performance goal of **89%** with expected clinical success rate of **94%**. These assumptions are based in the following meta-analyses of clinical success for closure of a defect:

• 20 publications representing 2257 patients: 93.9% (95% CI 88.6%-97.6%)

The null and alternative hypotheses for the primary effectiveness endpoint are as follows:

Ho: $\pi_1 \le 89\%$ *Ha*: $\pi_1 > 89\%$

where π_1 is the probability of clinical success.

We hypothesize that the **serious adverse event (SAE) rate** related to MANTISTM clip or the endoscopic clipping portion of the procedure will be lower than the performance goal of **19%** with expected related SAE rate of **10%**. These assumptions are based in the following meta-analyses of clinical success for closure of a defect:

• 9 publications representing 1019 patients: 9.8% (95% CI 3.7%-18.5%)

The null and alternative hypotheses for the primary endpoint are as follows:

Ho: $\pi_1 \ge 19\%$ *Ha*: $\pi_1 < 19\%$

where π_1 is the probability of an related SAE.

Using an exact test with an alpha level of 0.05, 217 subjects enrolled will provide at least 80% power for the performance and safety metrics. An additional 10% will be added for attrition, so total enrollment will be 240 subjects. These tests will only be performed for cases in the continued enrollment cohort

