4 GENERAL STATISTICAL METHODS

4.1 Analysis Sets

Enrolled Cohort

A subject is considered enrolled after signing the study-specific ICF. Subjects who sign the ICF, but subsequently do not meet one or more of the eligibility criteria provided in Section 8.1 and Section 8.2 will be considered screen failures and excluded from the study.

Intent-to-Treat Cohort (ITT)

This cohort consists of enrolled subjects who are planned to have a MANTISTM clip placed regardless if they met I/E criteria.

Treated Cohort

The treated cohort is a subset of the ITT subjects who have a MANTISTM clip placed.

ADDITIONAL DATA ANALYSES

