7.3 Rules and Definitions

- Binary event rates (proportions) will be reported on a per-patient basis.
- The last follow-up date will be the latest of the following dates for each patient: date of an adverse event, procedure date, follow-up visit date, and device event date.
- Serious Adverse Event will be defined as an adverse event that:
 - Led to death
 - Led to a serious deterioration in the health of the subject that either resulted in:
 - a life-threatening illness or injury, or
 - a permanent impairment of a body structure or a body function, or

- in-patient hospitalization or prolonged hospitalization (of an existing hospitalization), or
- medical or surgical intervention to prevent life-threatening illness or injury or permanent impairment to a body structure or a body function
- o Led to fetal distress, fetal death, or a congenital abnormality or birth defect.
- When calculating rates of adverse events, missing and partial dates will be handled as follows:

Partial Date Description	Action Taken
Entire onset date is missing	The procedure date will be used for the
	onset date.
The month and the day of the month are	January 1 will be used for the month and
missing but the year is available	day of the onset date. However, if the
	imputed date falls before the procedure
	date, then the procedure date will be used
	for the onset date.
Day is missing, but the month and year are	The 1 st will be used as the day of the onset
available	date. However, if the imputed date falls
	before the procedure date, then the
	procedure date will be used for the onset
	date.

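### Does the 10% attrition allowance conflict with analysis sets that keep subjects lost to follow-up?

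*Protocol*

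**What the plan says.** The sizing in Protocol 12.1.1.3 reads: "Using an exact test with an alpha level of 0.05, 217 subjects enrolled will provide at least 80% power for the performance and safety metrics". The next sentence adds the allowance: "An additional 10% will be added for attrition, so total enrollment will be 240 subjects". SAP 3.1.3 repeats both and gives one-sided hypotheses: success above 89% (94% expected) and related SAEs below 19% (10% expected).

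Protocol 12.2.1 and SAP 4.1 define the same three sets. Enrolled depends on consent. For ITT: "This cohort consists of enrolled subjects who are planned to have a MANTISTM clip placed regardless if they met I/E criteria". For Treated: "The treated cohort is a subset of the ITT subjects who have a MANTISTM clip placed". None has a follow-up condition, and neither document says which set carries the primary tests.

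On missing data, SAP 7.3 asks for binary rates per patient and has one imputation rule, for adverse event onset dates: "When calculating rates of adverse events, missing and partial dates will be handled as follows". Protocol 11.8 deals with a missed final visit: "If the last follow-up visit was not completed, the reason will be noted on the study completion form", plus a deviation form. Protocol 10.3 requires at least three documented contact attempts before a subject is declared lost. Protocol 10.2 requires every enrolled subject to be accounted for and allows use of data collected before withdrawal.

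**The concern.** An attrition allowance makes sense only if lost subjects leave the test, so that about 217 remain. Screen failures do not count toward enrollment (Protocol 10.1), so the allowance must cover losses after the procedure. Yet a treated subject who cannot be reached at day 30 belongs to all three sets.

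If the sets are taken as fixed denominators, such a subject has not shown sustained closure to 30 days and so is not a success, but also has no recorded SAE and so has no event. The same person would then count against the device on effectiveness and for it on safety, and neither matches the sizing. In an open-label, single-arm study against fixed goals, with no independent events or data committee (Protocol 21.1), a denominator chosen after the results are known could decide whether a goal is met.

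**Working it through.** **Inputs.** Goals 89% and 19%, expected rates 94% and 10%, exact test at 0.05, 217 subjects before attrition, 10% attrition, 240 enrolled (Protocol 12.1.1.3, SAP 3.1.3). Assumptions: the test is one-sided, as the hypotheses are written; every subject has an applicable outcome; and, except in step 5, loss is unrelated to outcome.

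**Formulas.** Effectiveness passes with at least r successes, where r is the smallest value with P(Bin(n, 0.89) ≥ r) ≤ 0.05; power is P(Bin(n, 0.94) ≥ r). Safety passes with at most c events, where c is the largest value with P(Bin(n, 0.19) ≤ c) ≤ 0.05; power is P(Bin(n, 0.10) ≤ c).

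**1. The plan's own figure.** At n = 217, r = 201 and c = 31. Effectiveness has type I error 4.9% and power 84.1%; safety has 4.3% and 98.3%. The claim of at least 80% power holds. For attrition, 217/0.9 = 241.1 and 217 × 1.1 = 238.7; the stated 240 lies between them. So 217 is the number expected to remain for analysis.

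**2. Lost subjects excluded, as the sizing implies.** 240 × 0.9 = 216, so 24 are lost. At n = 216, r = 201 and c = 31. Effectiveness has type I error 3.0% and power 77.3%; safety has 4.5% and 98.4%. The expected result, 0.94 × 216 ≈ 203 successes, gives p = 0.009. The fall from 84.1% to 77.3% comes from one subject: r stays at 201 while n drops by one. At 12 losses (n = 228, r = 211) power is 85.6%. Averaged over random 10% loss it is 80.7%.

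**3. Lost subjects counted as failures (not in the plan).** At n = 240, r = 222, so 18 failures are allowed. With 24 losses the best possible result is 216/240 (p = 0.356), and 203/240 gives p = 0.986. From 19 losses on, the test cannot pass. This rule would make the allowance self-defeating.

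**4. Lost subjects kept as event-free for safety (not in the plan).** At n = 240, c = 35. Type I error with 24 losses is P(Bin(216, 0.19) ≤ 35) = 16.9%. That is a ceiling: it supposes that no related SAE in a lost subject is known before loss. If 50%, 75% or 90% of them are known (assumed shares; the documents give none), it is 9.2%, 6.5% or 5.2%. The choice of denominator changes the result only for 32 to 35 events among 216, which has probability 1.4% at the expected 10% rate.

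**5. If loss depends on outcome.** Suppose overall success is exactly 89%, 10% are lost at random in number, and the lost succeed at rate q. Retained subjects then succeed at (0.89 − 0.1q)/0.9, which is 90.0% for q = 0.80 and 91.1% for q = 0.70. With the lost excluded, effectiveness type I error is 9.7% and 22.3%.

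**6. One-sided 0.025.** The SAP revision history says "The sample size calculation was performed using 0.025 alpha, so nothing else changed", while the current text says 0.05. At 0.025, 240 subjects need 224 successes, so 24 losses still exceed the 16 failures allowed. The contrast between the rules is unchanged.

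**The case for a change.** The strongest case for a change is that exclusion is only implied. No evaluable set exists, and an ITT label can suggest that everyone stays in. Few losses would matter if they counted as failures: 5 of 240 would cut effectiveness power from 86.6% to 45.0%. Two or three sentences would close the gap, with no added subjects. A tipping-point table would show how fragile a pass is: with 203 of 216 successes and 24 lost, up to 5 of the 24 could be failures (222/240, p = 0.046), and a sixth gives p = 0.073.

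What stands is that the plan names neither the primary set nor a missing-outcome rule, and that exclusion is biased if loss depends on outcome (step 5).

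What does not stand is the contradiction. A set fixes who belongs; it does not turn an unknown outcome into a failure or a non-event. The clash between the endpoints also depends on how silence is read: for the bleeding part of clinical success, no recorded event would give a success. Writing down exclusion would only restate what the sizing implies. A natural refinement, which counts failures recorded before loss but drops the other lost subjects, would be worse because failures stay in while successes leave. At 10% random loss, power would fall from 80.7% to 78.0%, 75.0% or 68.8% if 25%, 50% or 100% of the lost subjects' failures were recorded. The tipping-point table is a useful extra, but anyone can work it out from the counts of successes and losses.

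**Conclusion.** The concern does not call for a change. The documents leave a detail unstated, but their sizing supports one sensible reading: each primary proportion is computed over subjects whose outcome is known. On that reading both tests keep their nominal size when loss is unrelated to outcome (3.0% and 4.5% at 24 losses), and safety power is 98.4%. Effectiveness power is 77.3% at exactly 24 losses and 80.7% averaged over random 10% loss, so the shortfall from 80% comes from the steps of the exact test and not from how losses are handled.

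The large figures (p = 0.986, type I error near 17%) belong to rules that the plan does not state, and the safety figure is a ceiling. They also take the full 10% as the actual loss. That figure is an allowance; follow-up is one telephone call at 30 ± 5 days with repeated contact attempts. The conclusion rests on one-sided tests, an applicable outcome for every subject, and loss that is not strongly tied to failure. If many subjects are lost, that last assumption deserves comment in the report.

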12.2.1 Analysis Sets

Enrolled Cohort

A subject is considered enrolled after signing the study-specific ICF. Subjects who sign the ICF, but subsequently do not meet one or more of the eligibility criteria provided in Section 8.1 and Section 8.2 will be considered screen failures and excluded from the study.

Intent-to-Treat Cohort (ITT)

This cohort consists of enrolled subjects who are planned to have a MANTISTM clip placed regardless if they met I/E criteria.

Treated Cohort

The treated cohort is a subset of the ITT subjects who have a MANTISTM clip placed.

12.3 Data Analyses

All statistical analyses will be done using The SAS System software, version 8 or higher (Copyright © 2000 SAS Institute Inc., SAS Campus Drive, Cary, North Carolina 27513, USA. All rights reserved).

12.3.1 Other Endpoints/Measurements

- Technical success at placement defined as ability to deploy the endoscopic clips in satisfactory position.
- Post procedural bleeding, defined as a severe bleeding event that required hospitalization, a blood transfusion (>5 units), or another invasive intervention (angiographic or surgery) within 30 days after the study clip placement.
- For active bleeding hemostasis cases only
 - Rate of patients requiring additional modalities of hemostasis.
 - Report of hemostasis of active bleeding 7 days after the index study procedure, defined as ability to stop the active bleed at the time of the study procedure and/or with additional clipping procedures to provide hemostasis of continued or recurrent bleeding within 7 days of the index study procedure

12.3.2 Baseline Data

Subject demographics and medical history will be summarized using descriptive statistics (e.g., mean, standard deviation, n, minimum, maximum) for continuous variables and frequency statistics for discrete variables.

12.3.3 Procedure Data

Procedure data including qualitative evaluation will be collected and reported using descriptive statistics (e.g., mean, standard deviation, n, minimum, maximum) for continuous variables and frequency statistics for discrete variables.

12.3.4 Post-Procedure Data

Post-procedure information will be collected as detailed in Table 11-1.1 Data Collection Schedule and will be summarized using descriptive statistics for continuous variables (e.g., mean, standard deviation, n, minimum, maximum) and frequency statistics for discrete variables.

12.3.5 Interim Analyses

12.3.6 There will be no formal interim analyses performed. irlSubgroup Analyses

Stratified analyses will include tabulating the primary and select secondary endpoints by gender, polyp location, polyp size, or use of periprocedural antithrombotic medications.

12.3.7 Justification of Pooling

The analyses will be performed using data pooled across institutions. An assessment of the poolability of patients across sites will be made by fitting generalized linear models with site as the factor of interest and the primary endpoints as the outcome variable.

12.3.8 Multivariable Analyses

Multivariable analyses may be performed to assess the effect of potential predictors on the primary endpoint.

12.3.9 Changes to Planned Analyses

Any changes to the planned statistical analyses made prior to performing the analyses will be documented in an amended Statistical Analysis Plan approved prior to performing the analyses.

13 Data Management

13.1 Data Collection, Processing, and Review

Subject data will be recorded in a limited access secure electronic data capture (EDC) system.

The clinical database will reside on a production server hosted by Medidata. All changes made to the clinical data will be captured in an electronic audit trail and available for review by the sponsor or its representative. The associated Rave software and database have been designed to meet regulatory compliance for deployment as part of a validated system compliant with laws and regulations applicable to the conduct of clinical studies pertaining to the use of electronic records and signatures. Database backups are performed regularly.

The Investigator provides his/her electronic signature on the appropriate electronic case report forms (eCRFs) in compliance with local regulations. A written signature on printouts of the eCRFs must also be provided if required by local regulation. Changes to data previously submitted to the sponsor require a new electronic signature by the Investigator acknowledging and approving the changes.

Visual and/or electronic data review will be performed to identify possible data discrepancies. Manual and/or automatic queries will be created in the Medidata EDC system and will be issued to the site for appropriate response. Site staff will be responsible for resolving queries in the database.

Access to the clinical database will be changed to "Read only" after data is either "Hard Locked" or "Entry Locked". Once acceptance of the final report or finalization of publications (as applicable) is received, final database storage and archiving activities can begin. Once the closeout activities are completed a request to IT is submitted to have the "Database Locked" or Decommissioned and database access revoked.

13.2 Data Retention

The Principal Investigator or his/her designee or Investigational site will maintain all essential study documents and source documentation that support the data collected on the study subjects in compliance with applicable regulatory requirements.

The Principal Investigator or his/her designee will take measures to prevent accidental or premature destruction of these documents. If for any reason the Principal Investigator or his/her designee withdraws responsibility for maintaining these essential documents, custody must be transferred to an individual who will assume responsibility and BSC must receive written notification of this custodial change. Sites are required to inform Boston Scientific in writing where paper or electronic files are maintained in case files are stored off site and are not readily available.

13.3 Technical Source Forms

A Technical Source Form (TSF) may be developed by Boston Scientific or by the investigational site to capture protocol required data elements that are not duplicated in any other source documents. This form is to be used by the study sites as a source document. A Boston Scientific representative may complete the TSF at the request of the Principal Investigator. The TSF will be reviewed and signed for approval by the Principal Investigator or his/her designee at the end of each procedure.

14 Deviations

An Investigator must not make any changes or deviate from this protocol, except to protect the life and physical well-being of a subject in an emergency. An investigator shall notify the sponsor and the reviewing IRB/EC/REB, and the regulatory authority if applicable of any deviation from the investigational plan to protect the life or physical well-being of a subject in an emergency, and those deviations which affect the scientific integrity of the clinical investigation. Such notice shall be given as soon as possible, but no later than 5 working days after the emergency occurred, or per prevailing local requirements, if sooner than 5 working days.

Deviations from the investigational plan, with the reason for the deviation must be documented and reported to the sponsor using EDC. Sites may also be required to report deviations to the IRB/EC/REB, and the regulatory authority, per local guidelines and national/government regulations.

Deviations will be reviewed and evaluated on an ongoing basis and, as necessary, appropriate corrective and preventive actions including IRB/EC/REB/Regulatory Authority/FDA

notification, site re-training, or site discontinuation/termination) will be put into place by the sponsor.

The sponsor will not approve protocol waivers.

15 Device Accountability

